1.3 Schedule of Activities

Table 1-1Schedule of Activities (SoA) – Part 1 and Part 2

Decos Jame / A second sec	S	Cycle 1 [†]					
Procedure/Assessment	Screening	Treatment Period					Rest Period
Day(s)	-28 to -2	-1	1	2 to 7	8 to 13	14	15 to 21
Week(s)	-4 to	0		1		2	3
Informed consent ^c	Х						
In-house stay (optional)			Х				
Inclusion/exclusion criteria	Х	Х					
Patient Diary ^d			Х	Х	Х	Х	
Phone call ^e	Х	Х	Х	Х	Х	Х	X
Routine Clinical Procedures							
Demographics	Х						
Medical history (including any available historical genetic assays conducted to identify genetic variations [all patients] and Gleason score for mCRPC patients only) ^f	Х	х					
Physical examination ^g	Х		Х				
Height and weight ^g	Х						
Vital signs ^h	Х		Х	Х		Х	
ECG ⁱ	Х		Х	Х		Х	
Prior and concomitant medications ^j	Х	Х	Х	Х		Х	

Procedure/Assessment	Screening				Cycle 1 [†]			
Troceure/Assessment	Screening	Treatment Period					Rest Period	
Day(s)	-28 to -2	-1	1	2 to 7	8 to 13	14	15 to 21	
Week(s)	-4 to	0		1		2	3	
Routine Safety Measure								
Urinalysis ^k	Х		Х	Х		Х		
Hematology ^{k, 1}	Х		Х	Х		Х		
Clinical chemistry ^{k, m}	Х		Х	Х		Х		
Coagulation ^{k, n}	Х		Х	Х		X		
Testosterone (mCRPC) °	Х		Х					
Serology screen ^p	Х							
SARS-CoV-2 screen (optional; at Investigator's discretion) ^q	Х							
FSH testing ^r	Х							
Pregnancy test ^s	Х		Х					
Adverse event ^t	Х	Х	X	Х		X		
Efficacy Measurements								
PSA ^u	Х		Х					
Tumor imaging (RECIST v1.1) CT/MRI v	Х							
Bone scan (PCWG-3) v	Х							
SRE and SSE evaluation	Х	Х	Х	Х		Х		
ECOG performance status	Х		Х					
EORTC-QLQ-C30 w	Х							
BPI-SF questionnaire ^w	Х							
FACT-P (mCRPC patients only) w	Х							
PEQ ×				Х				
Survival status ^y								
Pharmacokinetic Measurement								
Blood sample for PK ^z			Х	X		Х	Х	

Procedure/Assessment	S	Cycle 1 [†]							
Procedure/Assessment	Screening		Treatment Period						
Day(s)	-28 to -2	-1	1	2 to 7	8 to 13	14	15 to 21		
Week(s)	-4 to	0		1		2	3		
Pharmacodynamic Biomarker Assessment	Pharmacodynamic Biomarker Assessment								
Blood sample for biomarkers ^{aa}	Х		Х				X ^z		
Archived tissue collection if available (Optional) ^{bb}	Х								
Fresh tissue biopsy after Cycle 3 treatment (Optional)									
Treatment Administration	Treatment Administration								
NOX66 ^{cc}			Х	Х	Х	Х			
EBRT (1-10 days) ^{dd}				Х					

Procedure/Assessment Day(s)						Safety							
		2		Cycle 2 Onwa 3‡			4 [§]			5	EOT/ED ^a	Follow-up	Follow-up ^b

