At a minimum, imaging of the chest, abdomen and pelvis should be performed using consistent imaging modality (computerized tomography [CT] or magnetic resonance imaging [MRI]). As far as possible, the same imaging method should be used for the patient throughout the study.

- W. Questionnaire to be completed at Screening, Day 1 of Cycle 3, Day 1 of Cycle 5 followed by every 4 cycles thereafter (e.g., Cycle 9, Cycle 13 etc.) and at the EOT/ED Visit. Questionnaire to be completed prior to performing any other study visit assessments on the day of the visit.
- x Questionnaire to be completed on Day 2 of Cycle 1, Day 1 of Cycle 3 and at the EOT/ED Visit. Questionnaire to be completed prior to performing any other study visit assessments on the day of the visit (excluding predose clinical laboratory assessment for Cycle 1 Day 1 which may be completed within 3 days prior to Day 1).
- ^{y.} May be an in-person visit or a phone call. Only applicable to patients who have met disease progression.
- ^{z.} Pharmacokinetic samples are to be obtained on Days 1, 2, 6, 14 and 15 of Cycle 1, and Days 1 and 8 of Cycles 2 and 3. See PK sampling schedule in Table 1-3. For Part 2, PK sampling will only be performed for the first 10 patients enrolled for each tumor group (mCRPC, breast cancer or non-small-cell lung cancer).
- aa. Pharmacodynamic blood samples to be collected at Screening or Cycle 1 on Days 1 and 15, prior to dosing on Day 1 of Cycle 3 (during the rest period after patients have completed 7-days of NOX66 treatment in Cycle 2, or predose on Day 1 of Cycle 3) and at the EOT/ED Visit. See PD sampling schedule in Table 1-4.
- ^{bb.} Patients will be asked whether they are willing to provide both archival and fresh tissue biopsy samples OR only fresh tissue biopsy if they do not have archival tissue samples. Available archival tissue samples will only be requested if a fresh tissue biopsy is collected after Cycle 3. Provision of a fresh biopsy sample and/or an archival tissue sample is optional. See Table 1-5.

- ^{cc.} On days when study drug and EBRT are to be administered, it is advisable that NOX66 is given at least 1 hour prior to EBRT. Twice daily of NOX66 dosing should occur at least 10 hours apart. Where 2 suppositories are administered per dosing, each suppository will be administered at least 5 minutes apart.

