Additional EBRT at the dose levels/fractions stated above may be given during the study. However, should additional EBRT be considered necessary during the study (Cycle 2 onwards), the Investigator should communicate this to the Medical Monitor for team acknowledgment since extra doses could impact study results.

The expected study duration for each patient from initial administration of NOX66 until the last study visit is determined by the number of treatment cycles each patient receives plus the follow-up period, which is from the last dose of NOX66 on study until death or the patient is lost to follow-up.

The study will finish when the last patient enrolled in Part 2 completes 6 months of treatment and all patients receiving study drug at that time will be switched to the NOX66 compassionate access program. Those patients on the compassionate access program will continue to receive NOX66 treatment until disease progression or unacceptable toxicity. The patients will be followed until death, or the patient is lost to follow-up.

There will be a Screening period of up to 27 days (Days -28 to -2). Each patient will attend the study center on Day -1 of Cycle 1 for eligibility assessments and on all PK days (Cycle 1: Days 1, 2, 6, 14 and 15; Cycles 2 and 3: Days 1 and 8). Patients in Part 1 may require an overnight stay on Day 1 of Cycle 1. On Days 1, 2, 6 and 14 of Cycle 1 and Day 1 of Cycles 2 and 3, the NOX66 morning administration will occur at the study center under medical supervision. During these days blood samples for PK analysis will be collected as per the

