8.1.5 Clinical Outcome Assessment

A Clinical Outcome Assessment is any assessment that may be influenced by human choices, judgement or motivation and may support either direct or indirect evidence of treatment benefit. Patient reported outcome is one of these types of Clinical Outcome Assessments.

Patient reported outcome, an umbrella term referring to all outcomes and symptoms, are directly reported by the patient. Patient reported outcomes have become a significant endpoint when evaluating effectiveness of treatments in clinical trials.

Questionnaires are to be completed before any other study assessments performed on the day of the visit.

The following PRO instruments will be administered for analysis of the PRO endpoints in this study:

• European Organisation for Research and Treatment of Cancer Quality of Life Questionnaire for Cancer Patients (EORTC-QLQ-C30)

The EORTC-QLQ-C30 is a well-established PRO questionnaire developed to monitor health-related Quality of Life (QoL) outcomes among cancer patients (Section 10.6). The questionnaire assesses important functioning domains (e.g., physical, emotional, social) and common cancer symptoms (e.g., fatigue, pain, nausea, vomiting, appetite loss). The questionnaire will be completed at Screening, on Day 1 of Cycles 3 and 5, followed by every 4 cycles thereafter (e.g., Cycle 9, Cycle 13 etc.), and at the EOT/ED Visit (Table 1-1 [Parts 1 and 2]).

• Brief Pain Inventory – Short Form (BPI-SF)

Worst pain, general pain and pain's interference with daily life will be assessed during the study drug using the BPI-SF (Section 10.7). The questionnaire will be completed at Screening, on Day 1 of Cycles 3 and 5, followed by every 4 cycles thereafter (e.g., Cycle 9, Cycle 13 etc.), and at the EOT/ED Visit (Table 1-1 [Parts 1 and 2]). The BPI-SF comprises a total of 15 items measuring 2 domains: pain severity and pain interference. Items measuring pain severity (including 'worst pain') are rated on an 11-point numeric rating scale ranging from 0=No pain to 10=Pain as bad as you can imagine. All BPI-SF items are measured using a 24-hour recall period.

• Functional Assessment of Cancer Therapy – Prostate (FACT-P)

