8.1.6 Morphine Administration and Analgesic Use

The dose and frequency of morphine administration and analgesic use will be assessed at each on-site study visit based on the patient's concomitant medication use assessment.

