9.4.1 General Considerations

The main aims of the study are to assess the safety, tolerability, efficacy, PK and PD profiles of idronoxil (and selected metabolites) and EBRT in combination with NOX66 in patients with prostate cancer and other solid tumors.

Concomitant medications, treatment exposure and study drug compliance will be summarized by dose cohort for Part 1 and by treatment arm for Part 2. All summaries will be based on the Safety Analysis Set.

Continuous data will be summarized using the number of patients (n), mean, standard deviation, median, 25th and 75th percentiles, minimum and maximum. Categorical data will be summarized using frequency tabulations (number and percentage of patients).

Unless specified, no formal statistical hypothesis testing will be conducted and all analyses will be descriptive. Two-sided 95% confidence intervals (CIs) will be presented alongside all point estimates to access precision.

Baseline will be defined as the last measurement obtained prior to the first administration of NOX66.

All statistical analysis will be performed using Statistical Analysis Software (SAS[®]) Version 9.3 or higher.

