9.4.7.2 Efficacy of NOX66

The following efficacy analysis will be conducted for the patients enrolled to Part 1 and Part 2 of the study. All analyses are based on the FAS. Results will be summarized by dose cohort (Part 1) or treatment arm (Part 2).

For patients with mCRPC, the change in PSA from baseline will be summarized by dose cohort (Part 1) or treatment arm (Part 2, Arm 1) assessed using samples collected on Day 1 of Cycles 1 to 5, every second cycle thereafter (i.e., Cycles 7, 9, 11 etc.), at the EOT/ED Visit and at the 6-, 9- and 12-month Follow-up visits for all patients including those that discontinued for any reason other than disease progression. A PSA response will be considered as a PSA value reduction \geq 30% from baseline at the end of Cycles 3 and 6. A PSA reduction from baseline at any time point will also be assessed as a secondary objective.

Overall response rate, defined as the percentage of patients with CR and PR, will be assessed based on change from baseline imaging (RECIST v1.1 and PCWG-3 criteria for measurable or evaluable lesions). The number and proportion of responders (CR and PR) will be presented along with the exact 95% CI (Clopper-Pearson) for the time points after Day 1. Patients are allowed to continue study treatment until disease progression, unacceptable toxicity, withdrawal of consent, start of a new anticancer therapy, withdrawal of the patient by the Investigator or termination of the study by Sponsor. Tumor imaging assessment will be continued as scheduled for the patients who are discontinued from the study for reasons other than disease progression (see Section 8.1.3). The best overall response (CR, PR, SD or progression) will be summarized.

The change in ECOG from baseline will be summarized by dose cohort (Part 1) or treatment arm (Part 2) over time. The change in pain severity and pain interference with daily activities from baseline will be summarized by dose cohort (Part 1) or treatment arm (Part 2) over time. The number and proportion of patients with a pain response (\geq 2-point reduction in pain severity and no additional opioid use) will be summarized over time along with the exact 95% CIs

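### Pain and quality-of-life baselines are taken only at Screening, 2 to 28 days before first dose, so change before any study treatment enters the uncontrolled change scores

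*Combined protocol and SAP*

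**What the plan says.** Footnote w to Table 1-1 (Section 1.3) covers the BPI-SF, QLQ-C30 and FACT-P: "Questionnaire to be completed at Screening, Day 1 of Cycle 3, Day 1 of Cycle 5 followed by every 4 cycles thereafter". Section 8.1.5 agrees for each instrument: "The questionnaire will be completed at Screening, on Day 1 of Cycles 3 and 5, followed by every 4 cycles thereafter". The rows of Table 1-1 show the same pattern, with a mark at Screening and none in Cycle 1. For the pain instrument, Section 8.1.5 adds: "All BPI-SF items are measured using a 24-hour recall period".

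On the window, Section 4.1 says: "There will be a Screening period of up to 27 days (Days -28 to -2". The same section has every patient attend on Day -1 and again on Cycle 1 Day 1.

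Medication is followed more closely. The Table 1-1 row "Prior and concomitant medications" is marked at Screening, Day -1 and Day 1, and Section 8.1.6 says: "The dose and frequency of morphine administration and analgesic use will be assessed at each on-site study visit". Section 6.5 requires start and end dates, dose and frequency.

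Section 9.4.1 gives one general rule: "Baseline will be defined as the last measurement obtained prior to the first administration of NOX66". Section 9.4.7.2 defines pain response as at least a "2-point reduction in pain severity and no additional opioid use", to be reported over time with exact 95% confidence intervals.

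Section 8.2.2.4.1 permits analgesics. Neither that section nor the eligibility criteria in Sections 5.1 and 5.2 require a stable analgesic regimen before first dose.

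**The concern.** Under the general baseline rule, baseline pain is the Screening value because no later predose value exists. That value is one day's recall and can be four weeks old. Patients enter with lesions for which EBRT is being considered, so pain and analgesia may well move while they wait. With no control arm, nothing removes that movement from a change score.

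The response rule also joins two components that may have different reference dates. Pain is referenced to Screening. Opioid use, if the same general rule is applied to it, is referenced to Day 1, when medication was last reviewed before dosing. A patient whose analgesia was increased between those dates could then show a fall in pain and no added opioid, although nothing changed after treatment began.

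At stake are the pain-response proportion and the change scores on three questionnaires. These serve two secondary objectives, on pain and on quality of life.

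**Working it through.** **1. The plan's own figure.** Days -28 to -2 inclusive: -2 - (-28) + 1 = 27 days. This reproduces the length stated in Section 4.1.

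**2. Age of the baseline at first dose.** The schedule has no Day 0, so Day -k lies k days before Day 1. The latest Screening day, Day -2, gives 2 days. The earliest, Day -28, gives 28 days.

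**3. First post-baseline questionnaire.** Cycle 1 lasts 21 days and Cycle 2 lasts 14, so Cycle 3 Day 1 is 21 + 14 + 1 = Day 36, which is 35 days after Day 1.

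**4. Span of the first change score.** Shortest: 2 + 35 = 37 days. Longest: 28 + 35 = 63 days.

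**5. What the change score contains.** For any patient,

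(Cycle 3 Day 1 − Screening) = (Cycle 3 Day 1 − Day 1) + (Day 1 − Screening).

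The last term precedes both NOX66 and EBRT. Pain is not measured on Day 1, so the two terms cannot be separated afterwards.

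**6. Reference dates for the response rule.**

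| Component | Last predose record | Baseline under Section 9.4.1 |
|---|---|---|
| BPI-SF pain severity | Screening | Day -28 to Day -2 |
| Opioid use | Day 1 medication review | Day 1, if the general rule is applied; no section states a date |

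**7. Three hypothetical patients.** The scores are invented to show how the rule behaves. Each has a Screening BPI-SF before Day -10 and no change in analgesia after Day 1.

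| Patient | Screening | Day 1 | Cycle 3 Day 1 | Current pain baseline, opioid date = Day 1 | Current pain baseline, opioid date = Screening BPI-SF | Day 1 for both |
|---|---|---|---|---|---|---|
| A: opioid raised on Day -10 | 7 | 4 | 4 | fall 7 − 4 = 3, none added: responder | fall 3, opioid added: non-responder | fall 4 − 4 = 0: non-responder |
| B: non-opioid change or natural fall | 7 | 4 | 4 | fall 3: responder | fall 3: responder | fall 0: non-responder |
| C: pain worsens before dosing, no analgesic change | 4 | 7 | 4 | fall 4 − 4 = 0: non-responder | fall 0: non-responder | fall 7 − 4 = 3: responder |

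Patient A is misclassified only under one reading of the opioid date. Patient B is misclassified under both. Patient C is misclassified in the opposite direction.

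**The case against.** Five points can fairly be made for the plan.

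- **The opioid date is open.** The protocol does not say from when added opioid use is counted, and the dated medication record lets it be counted from the Screening BPI-SF. Section 9.4 leaves detail to a SAP finalised before database lock. A reader might infer that the plan does score opioid relief gained during Screening as response. The text does not support that: it can happen under one reading and not under the other. This stands. It does not help patient B, because non-opioid analgesics and natural fluctuation lie outside the rule.
- **The direction is not known.** A reader might also infer that response is biased upward. But eligibility requires documented progression, so pain may rise before dosing. Minimally symptomatic patients also qualify, and a patient whose baseline pain is below 2 cannot fall by 2 points. This stands.
- **EBRT confounds pain anyway.** It starts on Day 2, and Appendix 10 gives symptom relief and pain management as its purpose. No choice of baseline makes this a response to NOX66 alone. That stands too, but a Day 1 baseline would at least confine the change to the period after the combined regimen begins.
- **The endpoint is descriptive.** Section 9.1 tests no hypotheses, and neither the primary endpoints nor the dose-selection rule uses pain. This limits the consequence. The exact confidence interval still does not reflect a misplaced baseline.
- **QLQ-C30 and FACT-P differ.** Most QLQ-C30 items recall a week and FACT-P recalls 7 days, and neither has an opioid component. The 24-hour and opioid arguments therefore apply only to the BPI-SF. The age of the baseline applies to all three.

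**Conclusion.** The point holds as a weakness in baseline timing. For all three questionnaires the baseline is 2 to 28 days before first dose, and the first change score covers 37 to 63 days, of which the first 2 to 28 precede any study treatment. These figures follow from the schedule alone. Pre-treatment change in either direction therefore enters pain response and the change scores, with no control arm to remove it.

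Misclassification of opioid-driven relief is conditional. It needs an opioid increase after the Screening BPI-SF, relief that lasts to Cycle 3 Day 1 or later, and an opioid reference date of Day 1. If the Screening BPI-SF date is used instead, only non-opioid changes and natural fluctuation remain.

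The net direction and size cannot be derived, because the documents give no rate of analgesic change during Screening and no variability for pain scores. Assuming a distribution for the Screening-to-Day 1 change and reading off a tail would not give a false-responder rate. Such a tail ignores the opioid condition and persistence to Day 36, and counts only the falls.

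This affects secondary, descriptive endpoints. It is still worth correcting, because the remedy is cheap and a baseline not collected before first dose cannot be recovered.

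**What to change.** - In Table 1-1 (the three questionnaire rows), footnote w and Section 8.1.5, schedule the BPI-SF, QLQ-C30 and FACT-P (mCRPC only) predose on Cycle 1 Day 1, or on Day -1.
- Use that value as baseline for pain response and for every change score from these three questionnaires. The rule in Section 9.4.1 then selects it without amendment.
- In Section 9.4.7.2, the synopsis and the SAP, state that added opioid use is judged from the date of that same baseline questionnaire.

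Stating the opioid date alone would settle patient A but not B or C, and would leave the QLQ-C30 and FACT-P change scores as they are.

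The cost is a few minutes at a visit that already exists, plus the wording changes. The predose order under Table 1-1 already puts the questionnaires first, and no eligibility criterion uses the Screening scores, so the Screening administration can be moved rather than duplicated. Patients dosed before the change would keep their Screening baseline and should be identified as such in the summaries.

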1.3.1 Electrocardiogram Schedule

Table 1-2	Electrocardiogram Schedule: Part 1 (All Patients) and Part 2 (Only
	for First 10 Patients in Each Tumor Type)

Sampling Time Point	Cycle 1 Day 1	Cycle 1 Day 2	Cycle 1 Day 6	Cycle 1 Day 14	Cycle 2 Day 1	Cycle 3 Day 1
Predose	\mathbf{X}^{\dagger}	Х	X^\dagger	X^\dagger	X^\dagger	\mathbf{X}^{\dagger}
1 hour (+ 15 minutes)	Х		Х	Х	Х	Х
2 hours (+ 15 minutes)	Х		Х	Х		
3 hours (+ 15 minutes)	Х		Х	Х		
4 hours (+ 15 minutes)	Х		Х	Х		
6 hours (+ 15 minutes)	Х		Х	Х		
8 hours (+ 15 minutes)	X ^a					
12 hours (+ 15 minutes)	X ^a					

† Within 30 minutes prior to dosing to allow for sitting blood pressure if needed.

^a Only for Part 1.

NOTE: For patients who will not undergo PK sampling in Part 2 of the study, a single ECG will be collected predose on Day 1 of each cycle up to Cycle 3.

After Cycle 3 Day 1, ECGs will be taken predose (within 30 minutes prior to dosing to allow for sitting blood pressure if needed) for all patients in both study parts, on Day 1 of every second cycle thereafter (i.e., Cycles 5, 7, 9, 11 etc.) and at the EOT/ED Visit.

1.3.2 Pharmacokinetic and Pharmacodynamic Sampling Schedule for Part 1 and Part 2

Table 1-3Pharmacokinetic Sampling Schedule Following Morning Dose –
Part 1 (All Patients) and Part 2 (Only for First 10 Patients in Each
Tumor Type)

Sampling Time Point	Blood Volume (mL)		Cycle 1 Day 2*	-	-	Cycle 1 Day 15**	•	Cycle 2 Day 8***	Cycl e 3 Day 1 ^b	Cycle 3 Day 8 ^{b,} ***
Predose (within 15 minutes prior to dosing)	1 × 4	х	х	Х	Х	Х	X	Xc	X	Xc
0.5 hour (± 5 minutes)	1×4	Х		Х	Х					
1 hour (± 5 minutes)	1×4	Х		Х	Х					
2 hours (± 5 minutes)	1×4	Х		Х	Х		Х		Х	
3 hours (± 5 minutes)	1×4	X		Х	Х					
4 hours (± 5 minutes)	1×4	Х		Х	Х					
6 hours (± 10 minutes)	1×4	Х		Х	Х					
8 hours (± 15 minutes) ^a	1 × 4	Х								
12 hours (\pm 30 minutes; Prior to evening dose) ^a	1×4	Х								

^{a.} Only for Part 1.

^{b.} Cycle 3 Days 1 and 8 samples only for patients in Part 2.

^{c.} Can be collected at home.

* Sample to be collected approximately 12 hours post Day 1 evening dose.

** Sample to be collected approximately 12 hours post Day 14 evening dose.

*** Sample to be collected approximately 12 hours post Day 7 evening dose.

Table 1-4	Pharmacodynamic Sampling Schedule – Part 1 and Part 2 (All
	Patients)

Assay	Blood Volume (mL)	Screening/Cycle 1 Day 1 Predose ^c			End of Treatment/Early Discontinuation
Chemokines, cytokines and lipids ^a	1 × 4	Х	Х	Х	Х
Circulatory tumor DNA a,d	2×4	Х	Х	Х	Х

^a Plasma

^b Sample should be collected after the patient has completed 7 days of NOX66 treatment in Cycle 2 and prior to dosing on Day 1 of Cycle 3.

^c Baseline samples to be collected only after eligibility confirmation or on Day 1 prior to NOX66 administration.

^d Only at pre-selected sites that have peripheral blood mononuclear cell isolation capabilities in Australia and the United States of America.

Table 1-5Optional Archival Tissue Collection and Fresh Biopsy Sampling
Schedule – Part 1 and Part 2 (All Patients)

Assay	Screening	After Cycle 3 treatment
Archival tissue if available (Optional)	Х	
Fresh biopsy (Optional)		Х

NOTE: Available archival tissue samples will only be requested if a fresh tissue biopsy is collected after Cycle 3. Provision of a fresh biopsy sample and/or an archival tissue sample is optional.

2 Introduction

The term "study drug" throughout the protocol, refers to NOX66. In addition, the terms participant and patient are used interchangeably.

